Preliminary Telehealth Model for Intervention Delivery. The proposed intervention will begin with implementing routine screening for depression and suicidality in adult HIV care at the 3 study sites. The screening tools, the PHQ-2 and Columbia-Suicide Severity Rating Scale (C-SSRS), contain 8 items assessing depression and suicidality in the past month, including thoughts, intent, plan, and actions. The PHQ has been validated in Tanzania. We propose to validate several additional study measures in a preliminary validation study with 80 patients living with HIV and experiencing suicidal ideation: the HIV Stigma Scale (HSS), Beliefs About Medicines Questionnaire (BMQ), Illness Cognition Questionnaire (ICQ), Columbia-Suicide Severity Rating Scale (C-SSRS), self-Efficacy to Avoid Suicidal Action Scale (SEASA), Beck Hopelessness Scale-Short Form (BHS-SF), and Brief Reasons for Living Scale (BRFL).

Patients who endorse depressive symptoms only will receive brief supportive counseling to identify coping strategies and a referral for mental health services. Patients who screen positive for suicidal ideation (respond "yes" to any C-SSRS item) will be eligible for enrollment in the pilot clinical trial.

Once consented, the study team will assist patients to make a video call to the telehealth hub using a mobile phone. Video calls will be made using WhatsApp, a freely available, secure, and widely used mobile application with end-to-end encryption. Calls will be made free of charge (without data charges) using Wi-Fi hotspots made available at each study clinic. Patients who do not have an Internet-equipped phone will use study-owned phones. Private space will be provided in the research offices at each clinic for video calls

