Supplementary Aim: First, all study measures will undergo a thorough process of translation, backtranslation, and discussion to consensus with a team of bilingual researchers. Using the same recruitment procedures and eligibility criteria described in Aim 1, nurses will implement suicide screening during HIV clinic appointments. Patients (n=80) who screen positive for suicidality (i.e., respond "yes" to any C-SSRS item) will be notified of the research and, if interested, provide informed consent. Eligible participants who are not interested in participanting will receive referrals and resources for mental health support. After providing consent, participants will complete the translated survey measures administered by trained study staff. These data will be used to validate the study measures in the Tanzanian clinical context through evaluation of internal consistency (Cronbach's alpha and item-scale correlation), convergent validity among related measures, and confirmatory factor analysis. Participants will receive an incentive of 10,000 TZ shillings (\$4.50) to compensate for time and transport. Data collection for this Aim was completed in October 2022.

Aim 2: Refine content for the telehealth intervention with support from a study advisory board in Tanzania. The Duke PI will form an advisory board consisting of PLWH, nurses, mental health workers, administrators and local and regional government officials, to assist in refining the intervention. The advisory board will have approximately 15 members and will convene 3 times: 1) at the conclusion of Aim 1 to assist in refining the intervention prior to piloting by interacting with a prototype model, 2) midway through the clinical trial to review progress, and 3) at the conclusion of the trial to review and assist in interpreting findings. Key members of our previous KCMC advisory boards would be invited to continue their involvement for the current study.

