Assignment to condition. Upon completion of the baseline survey, participants will be individually randomized to receive either a brief Safety Planning Intervention (n=30), or the 3-session telehealth intervention (n=30). Participants will be randomized at a 1:1 ratio using a block randomization method (4 per block) to ensure equal sample sizes in each condition and to manage the flow of participants to the intervention condition. The allocation sequences will be prepared ahead of time using an online randomization program.

Intervention and control procedures. After randomization, participants will be guided to a private space and assisted to connect by video call to the nurse-counselor (based at KCMC). Upon connecting, control participants will receive the brief (20 minute) Safety Planning Intervention and intervention participants will complete the first of 3 telehealth-delivered counseling sessions. For intervention participants, the remaining sessions will be scheduled at two-week intervals. Patients unable to come to the clinic for followup sessions will be given the option to connect via video call or telephone call from the location of their choice. For participants in both conditions, prior to ending the call, the counselor will re-administer the C-SSRS and those at risk of suicide will be directly referred for psychiatric assessment and treatment to ensure their safety. Participants in both conditions will receive text message check ins from the counselors to inquire about their well-being and connect them to additional support as needed. Participants in both conditions will also have the opportunity to contact the telehealth counselors at any time during normal business hours for additional support throughout their participation in the study. These 'booster sessions' will be focused on assessing suicide risk, safety planning, and reinforcing prior session content.

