It was clear in the feedback from NIMH that, given all trial participants will have screened positive for suicidal ideation, the study team would need to provide additional support for the control condition and not just "treatment as usual" or a referral for services. A brief safety planning intervention is the most common brief intervention for suicidal ideation. It involves identifying internal coping strategies, external resources for support, and planning formaking the environment safe: https://www.sprc.org/sites/default /files/SafetyPlanningGuide%20Quick%20Guide%20for%20Clinicians.pdf. Safety planning has a strong global evidence base.

Duke's role in the research. As the home institution of the PI, [name], Duke will provide office space and IT services, consultative services, grants and finance management, and library support for the research study. Duke students and postdoctoral associates may take on supportive roles in the reserch and will be added to the IRB protocol as appropriate. Duke IT will assist with procurement and software needs for research computers and tablets. Statistical support will be provided by Duke statisticians at Duke Global Health Institute and the Duke University School of Nursing.

[name] role in the research will be to lead the training of study personnel, including the study coordinator and research assistants and nurse interventionists. [name] will help to establish research offices at the clinic sites, establish procedures for data collection and intervention delivery, oversee intervention delivery and data collection to monitor data quality, lead data analysis, and dissemination and reporting of research findings.

Selection of Subjects

• List inclusion/exclusion criteria and how subjects will be identified.

For Aims 1 and 2, clinic nurses will assist in identifying adults in HIV care at the study clinics who previously experienced suicidal ideation. Administrators, nurses and mental health workers will be recruited from the study clinics.

For the supplemental validation study and the Aim 3 clinical trial, clinic nurses will implement screening for suicidality in the clinics using the Columbia-Suicide Severity Rating Scale (C-SSRS), which contains 6 items assessing suicidal thoughts, intent, plan, and actions. Patients who screen positive for suicidality (i.e., respond "yes" to any C-SSRS item) will be notified of the research and, if interested, provide informed

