consent for enrollment in the clinical trial. Eligible participants who are not interested in participating will receive referrals and resources for mental health support. Patients who are not eligible for the clinical trial but who screen positive for depressive symptoms will provide informed consent and be offered a brief counseling session focused on Problem Management. Patients who undergo screening for suicide assessment may also be referred for qualitative interviews.

All study participants across all aims will be at least 18 years of age, fluent in Kiswahili or English, and able to provide informed consent to participate.

Subject Recruitment and Compensation

 Describe recruitment procedures, including who will introduce the study to potential subjects. Describe how you will ensure that subject selection is equitable and all relevant demographic groups have access to study participation (per 45 CFR 46.111(a) (3)). Include information about approximately how many DUHS subjects will be recruited. If subjects are to be compensated, provide specific prorated amounts to be provided for expenses such as travel and/or lost wages, and/or for inducement to participate.

For Aims 1 and 2, we will use purposive sampling, asking HIV clinic nurses to identify current clinic patients who previously struggled with suicidal ideation and identifying individuals who have undergone screening for suicidal ideation.

For the supplemental Aim and Aim 3, clinic nurses will screen all adults attending HIV clinic appointments, and all patients who meet the eligibility criteria and screen positive for suicidal ideation will be eligible to be enrolled in the study/clinical trial, with those screening positive for depressive symptoms only being referred for Problem Management+.

All study recruitment will occur in Moshi, Tanzania and will no include DUHS patients. Participants will receive an incentive of 10,000 Tanzanian shillings (approximately \$4.50) at each study contact at the clinic to compensate for their time and transportation costs. Intervention participants who connect to calls from a location other than the clinic will receive 10,000 TZ shillings if connecting via video call (to compensate for time and data costs) and 5,000 TZ shillings if connecting by telephone call (as incoming calls will not incur costs to participants).

Subject's Capacity to Give Legally Effective Consent

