 Describe endpoints and power calculations. Provide a detailed description of how study data will be analyzed, including statistical methods used, and how ineligible subjects will be handled and which subjects will be included for analysis. Include planned sample size justification. Provide estimated time to target accrual and accrual rate. Describe interim analysis including plans to stop accrual during monitoring. Phase I studies, include dose escalation schema and criteria for dose escalation with definition of MTD and DLT.

Qualitative data will be analyzed using a thematic approach based on grounded theory and the constant comparative method, a rigorous set of inductive procedures to identify and examine themes from textual data in a way that is transparent and reproducible. Interview transcripts will first be summarized in a qualitative memo, including representative quotes, and organized around a priori domains reflecting the components of the interview guides and CFIR. Next, the memos will be uploaded to NVivo software for coding. Within the broader domains, emerging themes from the interviews will be identified and added to a codebook to develop a coding structure. Each memo will be coded by 2 team members, inter-coder agreement will be calculated, and disagreements will be reconciled via consensus discussion with a 3rd team member. After coding, we will produce NVivo queries and analytic memos to synthesize content, compare participant characteristics, and draw deeper meaning on themes. Qualitative results will be synthesized with the input of the Tanzanian research team, developed into at least one research manuscript, and submitted for publication.

Scale validation will include evaluation of internal consistency of each instrument (Cronbach's alpha and item-scale correlation), convergent validity among related measures, and confirmatory factor analysis to assess whether the factor structure of the English version of manuscript is retained in the Tanzaniain clinical sample.

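### Does admitting the validation sample by a 'yes' on the C-SSRS undermine the validation of the C-SSRS itself?

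*Combined protocol and SAP*

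**What the plan says.** Under Design & Procedures, the preliminary telehealth model proposes to "validate several additional study measures in a preliminary validation study with 80 patients living with HIV and experiencing suicidal ideation" and lists the C-SSRS as one of seven such measures. The Supplementary Aim recruits "Patients (n=80) who screen positive for suicidality", defined as a 'yes' to any C-SSRS item. Selection of Subjects applies the same route to the trial: "For the supplemental validation study and the Aim 3 clinical trial, clinic nurses will implement screening for suicidality".

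On what is measured, the Supplementary Aim says that after consent "participants will complete the translated survey measures administered by trained study staff", and its next sentence says that these data serve the validation. The analyses are Cronbach's alpha, item-scale correlations, convergent validity and, in Data Analysis & Statistical Considerations, "confirmatory factor analysis to assess whether the factor structure of the English version of manuscript is retained". No screen-negative group is planned. The text does not say in so many words that the C-SSRS is repeated in the staff survey, and it does not remark on selection by the instrument being validated. Data collection for this aim was completed in October 2022.

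**The concern.** A scale is being validated only in people who scored above zero on it. Removing everyone who answered 'no' throughout induces negative dependence between the items: given that at least one answer is 'yes', a 'no' on one item makes a 'yes' on another more likely. Alpha, item-rest correlations and the correlations that feed the factor analysis all fall, even when every true loading is positive.

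If that happened, a low alpha or a poor model fit could be put down to the Kiswahili translation when the entry rule caused it. The coefficients could also be quoted for settings that the sample does not represent, such as the screening step, in which "clinic nurses will screen all adults attending HIV clinic appointments", or the end of a session, when "prior to ending the call, the counselor will re-administer the C-SSRS". Suicidality is a primary outcome of the trial, so evidence on its measurement matters.

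**Working it through.** **Inputs from the documents.** n = 80; k = 6 C-SSRS items (Selection of Subjects); entry by any 'yes'. The plan gives no derivation of 80, no target alpha and no factor model, so there is no plan figure to reproduce.

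**Assumed inputs.** Six binary items driven by one factor; loadings 0.7, 0.8 or 0.9; commonest item endorsed by 8%, 15% or 30% of all adults screened, the others at 75, 50, 40, 30 and 25% of that rate. There are 1.5 million simulated respondents in each of the nine cases.

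**Statistic.** Alpha = k/(k − 1) × (1 − sum of item variances / variance of the total), with k = 6.

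**Results with the commonest item at 15%:**

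| Loading | Alpha, all screened | Any 'yes', independent second administration | Loss | Any 'yes', screening answers reused |
|---|---|---|---|---|
| 0.7 | 0.610 | 0.567 | 0.04 | −0.047 |
| 0.8 | 0.725 | 0.669 | 0.06 | 0.327 |
| 0.9 | 0.829 | 0.767 | 0.06 | 0.612 |

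Over all nine cases, the loss on an independent second administration runs from 0.01 (0.553 to 0.538; loading 0.7, 8%) to 0.06 (0.829 to 0.767; loading 0.9, 15%). With reuse of the screening answers it runs from 0.16 to 0.98. The mechanism is real: six independent items endorsed by 10% each have alpha near 0 unselected and −3.1 after selection.

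**Second set of assumptions.** With item frequencies of 15/10/6/4/3/3% and 600,000 respondents per setting, alpha is 0.58 to 0.80 in all screened and 0.55 to 0.76 on an independent second administration. With 30/22/15/10/8/8%, it is 0.66 to 0.84 against 0.60 to 0.78. The losses are 0.03 to 0.06.

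**Carry-over between administrations.** Some is plausible when the same questions are asked twice. At the lower frequencies and loading 0.8, alpha in all screened is 0.69. It falls to about 0.56 if item-specific errors correlate 0.7 (loss 0.13) and to 0.52 if they correlate 0.84 (loss 0.17).

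**False second dimension.** The second eigenvalue is 1.09 to 1.19 when screening answers are reused and 0.78 to 0.95 on a fresh administration. With error correlation 0.84 and the weakest loading it just reaches 1.00. A clear artefact therefore belongs to reuse.

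**Sampling error at n = 80.** Feldt's limits for an observed alpha a are 1 − (1 − a)F, with F at the 97.5% and 2.5% points on n − 1 = 79 and (n − 1)(k − 1) = 395 degrees of freedom, that is 1.382 and 0.695. For a = 0.70: lower 1 − 0.30 × 1.382 = 0.59; upper 1 − 0.30 × 0.695 = 0.79. These limits are approximate for binary items. A loss of 0.06 is a little over half of the 0.11 between the estimate and its lower limit.

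**Which column applies.** The Supplementary Aim runs in order: nurse screens, patient consents, staff administer the translated measures, those data are used for validation. The C-SSRS is on the list of measures to be validated. The natural reading is the second-administration column.

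**The case for a change.** The strongest reply is that the plan leaves the deciding fact implicit. Whether the effect is slight or severe depends on which C-SSRS answers are analysed, and no sentence says so for this scale. Carry-over could push the loss beyond the sampling interval even with a fresh survey. Naming the administration and limiting the claim would cost two sentences. Convergent validity of the C-SSRS is affected by the same selection.

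Much of this stands as a matter of reporting. A competent report will say which administration was used and that the C-SSRS coefficients, convergent validity included, describe screen-positive patients. The plan does not prevent that, and it already names its population as patients with suicidal ideation.

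The rest does not carry over into a change. The plan proposes no sensitivity, specificity or other accuracy analysis, so there is no clinic-wide screening claim to withdraw. Clinic screening rests on any single 'yes', and re-administration after sessions serves risk referral; neither is described as using a summed or factor score. A general instruction to disregard low alpha or misfit would do harm: on a fresh survey a clear misfit is real evidence about structure, and discounting it would leave a validation that could not fail. Re-analysis in all screened adults would need item-level answers from people who had not consented, and the documents do not say that these were kept.

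**Conclusion.** The observation is correct, but it calls for no change. Alpha is a property of a scale in a population, and this population is the one the trial enrols, so a modestly lower value in screen-positives is the relevant one for baseline scores. On the natural reading the loss is about 0.01 to 0.06, inside the sampling error of 80 patients. With strong carry-over it could be 0.13 to 0.17 in the middle setting, which a report should bear in mind when interpreting a low value. No section sets an alpha or fit threshold or makes the trial depend on the result. The entry rule, the randomised comparison and the other six measures are untouched.

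This is a gap that analysts fill sensibly when they write up the aim. The conclusion rests on the C-SSRS having been repeated in the staff survey, and its size on assumed loadings, item frequencies and carry-over, none of which the documents give. If the nurse's screening answers were in fact analysed, a low alpha or misfit should not be read as failure of the translation.

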The telehealth hub will be located in the KCMC Psychiatry Clinic and will be staffed by two trained research nurses. The two study nurses will answer calls using study-provided tablets and will document patient care electronically, saved on a secure, password-protected electronic database. Nurses provide the majority of health care in Tanzania, including HIV and mental health care, and Moshi is home to many skilled nurses seeking career opportunities. In a setting where specialized mental health training is extremely rare, nurses are a natural fit to deliver a sustainable intervention. The telehealth model will allow for the delivery of all sessions by nurse-counselors at the central hub to efficiently reach patients at subsidiary regional HIV clinics.

Before the first call, the research assistant will gather patients' contact information, preferences for outreach in the event of a missed session, and information for an emergency contact. They will then connect to the telehealth hub and the nurse will begin the first of three counseling sessions. The initial intervention session will be approximately one hour in length, and the second and third sessions will each be approximately 30 minutes in length. Sessions will be held every two weeks to mirror the frequency of HIV clinic appointments for newly diagnosed patients. Patients unable to come to the clinic for follow-up sessions will be given the option to connect via video call or telephone call from the location of their choice. Additional support will be offered through weekly text message check ins and optional phone contacts and booster sessions. At the end of each session, the counselor will re-administer the C-SSRS and patients at acute risk of suicide will be accompanied to a mental health provider for further assessment. If the patient is unwilling to see a provider, the consulting psychiatrist and emergency contact will be called for support.

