Aim 3: Pilot test the telehealth intervention in a randomized controlled trial to assess feasibility, acceptability, and potential efficacy for reducing suicidality and enhancing HIV care engagement. To evaluate the intervention, the study team will enroll 60 PLWH in a Stage I pilot feasibility trial. Participants will be adults who experienced suicidal ideation in the past month seeking HIV care at one of the 3 study clinics. Using the same recruitment procedures and eligibility criteria described in Aim 1, nurses will implement depression and suicide screening during HIV clinic appointments. Patients who screen positive for depression, but not suicidality, will not be eligible for the clinical trial but will receive a brief supportive counseling module based on WHO's Problem Management+ and a referral for further mental health support. Patients who screen positive for suicidality (i.e., respond "yes" to any C-SSRS item) will be referred to study staff, notified of the research and, if interested, provide informed consent. Eligible participants who are not interested in participating will receive referrals and resources for mental health support.

After providing consent, participants will complete a baseline survey administered by trained study staff. Participants will receive an incentive of 10,000 TZ shillings (\$4.50) for each session at the clinic to compensate for time and transport. Participants who connect to calls from a location other than the clinic will receive 10,000 TZ shillings if connecting via video call (to compensate for time and data costs) and 5,000 TZ shillings if connecting by telephone call (as incoming calls will not incur costs to participants). Data collected at baseline will include measures of suicidality, HIV care engagement, and covariates such as stigma, social support, and quality of life. For measures not previously validated in Tanzania, the study team will complete a thorough linguistic and cultural translation process as established by Beaton et al., including back translation, validity checks, and piloting.

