Feasibility and acceptability of the intervention will be described by retention patterns, participant satisfaction, fidelity, and implementation cost. *Participant satisfaction* will be measured using the Client Satisfaction Questionnaire⁹³ at the 3-month survey and defined as a mean score \geq 3 on a 1-4 scale. *Fidelit y* to the manual will be measured by TQS and deemed acceptable if mean scores are \geq 3 on a 0-4 scale. *Co st* of the intervention will be tracked, including the time for training, supervision, and actual costs incurred.

Potential efficacy will be assessed by analyzing differences by condition in primary outcomes (suicidality, HIV care engagement, viral load) and secondary outcomes (depression, social support, quality of life). The trial will not be powered to detect significant intervention effects or stable effect sizes; however, we will conduct these analyses to examine the potential for effects in a larger trial. Mixed-effects regression will be used to model pre-post differences within and between arms using a time by condition model specification (time, condition, and time*condition). Individual-level random intercepts will be used to account for correlation due to repeated measurement. This mixed-effects regression approach allows us to control for baseline outcome values that may not be balanced between groups due to small sample size, and may improve precision of treatment effect estimates. We will also generate parameter estimates and ranges of values to estimate power for a future larger clinical trial study.

Data & Safety Monitoring

• Summarize safety concerns, and describe the methods to monitor research subjects and their data to ensure their safety, including who will monitor the data, and the frequency of such monitoring. If a data monitoring committee will be used, describe its operation, including stopping rules and frequency of review, and if it is independent of the sponsor (per 45 CFR 46.111(a) (6)).

The Duke PI [name] will receive guidance on research with patients at-risk of suicide in monthly mentoring meetings with [name], a recognized expert in the field of suicide prevention research. During these meetings, Drs. [name] and [name] will review safety data from the study, including trends in suicidal ideation and any reported instances of suicidal behavior or death by suicide

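### Every block is fixed at 4, and the size is printed, in a trial whose arms are easy to tell apart: a fully informed observer could be certain of 20 of 60 allocations on average; undisclosed, randomly ordered block sizes are a cheap safeguard.

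*Combined protocol and SAP*

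**What the plan says.** Under Assignment to condition: "Participants will be randomized at a 1:1 ratio using a block randomization method (4 per block"). Two purposes are given for blocking: "to ensure equal sample sizes in each condition and to manage the flow of participants to the intervention condition". On generation: "The allocation sequences will be prepared ahead of time using an online randomization program". Randomisation follows the baseline survey, and the target is 30 per arm.

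The arms are easy to distinguish. Control is one 20-minute safety-planning call. Intervention is a first session of about an hour, with two more at two-week intervals (Preliminary Telehealth Model; Intervention and control procedures).

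On who does what:
- Recruitment: "clinic nurses will screen all adults attending HIV clinic appointments" (Subject Recruitment and Compensation).
- Consent: patients who screen positive "will be referred to study staff, notified of the research and, if interested, provide informed consent" (Aim 3).
- Connection: "Once consented, the study team will assist patients to make a video call to the telehealth hub using a mobile phone" (Preliminary Telehealth Model).
- Delivery: "The telehealth model will allow for the delivery of all sessions by nurse-counselors at the central hub" (same section).

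The documents do not say who holds the sequence, whether it is central or per clinic, or whether the staff who obtain consent also see assignments.

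**The concern.** With a single known block size, the later places in a block are settled once one arm has used its two places. Because the arms are not disguised, anyone who follows earlier participants through their calls can keep that count. A recruiter who did so would sometimes know the next assignment before approaching a patient, which could influence whom they invite and when.

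Randomising after the baseline survey does not prevent this if the next assignment can be predicted. What is at stake is the between-arm comparison that Data Analysis & Statistical Considerations intends to carry into planning a larger trial. Fidelity and cost are not affected.

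**Working it through.** **Inputs.** From the documents: 60 participants (Aim 3); 1:1, blocks of 4, 30 per arm (Assignment to condition); 4 health centres (Study Setting) or 3 clinics (Aim 3), which matters only if lists are per clinic. Assumed: clinic shares, and the example sizes 4, 6 and 8.

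**1. The plan's own figure.** 60/4 = 15 blocks; 15 × 2 = 30 per arm. Reproduced.

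**2. Certain places, fully informed observer.** A block has six possible orders. In AABB and BBAA the third and fourth places are certain (2). In the other four orders only the fourth is (1). Mean = (2×2 + 4×1)/6 = 4/3 per block; × 15 = 20 of 60. Range 15×1 = 15 to 15×2 = 30.

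**3. Best guesses, same observer.** The chances of being right at places 1 to 4 are 1/2, 2/3, 2/3 and 1, which sum to 17/6. × 15 = 42.5 correct (70.8%), or 12.5 above the 30 expected by chance.

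**4. Less informed observers, fixed blocks of 4.**
- Size known, starting position unknown, all 60 seen: about 16 certain (simulation). A run of four like assignments, for example, places a block boundary in its middle, and the position is then known.
- Separate clinic lists: a clinic of n has floor(n/4) × 4/3 certain places, plus 1/3 if n leaves remainder 3. Three clinics of 20: 3 × 5 × 4/3 = 20. Four of 15: 4 × (3 × 4/3 + 1/3) = 17.3.
- One central list, only own-clinic assignments seen, position known: the two places that exhaust an arm and the place itself must all fall at that clinic, giving 20 × Σp³. Four equal clinics: 1.25. Three equal: 2.2. Shares of 70/20/10%: 20 × (0.343 + 0.008 + 0.001) = 7.0.

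**5. Randomly ordered 4, 6 and 8, one list totalling 60, whole list seen (simulation).**

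| Observer knows | Certain of 60 |
|---|---|
| Only the 30/30 target | about 1.5 |
| Set of sizes | about 1.5 |
| Set of sizes and that the list ends at 60 | about 2.8 |
| Every block boundary | about 15 |

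The best guess is right 67.9% of the time with the set of sizes known: 0.679 × 60 − 30 = 10.7 above chance. The fall from 12.5 is (12.5 − 10.7)/12.5 = 14%.

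**6. Possible bias (illustration).** Assume up to half of the certain places are filled by participants 0.5 SD from the mean on the baseline outcome, in opposite directions by arm, with baseline to follow-up correlation r of 0.3 to 0.7. With 20 certain places the baseline difference is at most 0.5 × 20/60 × 1.0 = 0.17 SD. In the planned time-by-condition model the bias in change is (1 − r) times that, with opposite sign: at most 0.7 × 0.167 = 0.12 SD. The chance standard error of the difference in change is √(2/30) × √(2(1 − r)): 0.31 SD at r = 0.3 and 0.20 SD at r = 0.7. This assumes that staff act only on certain places. Staff acting on best guesses would keep most of their advantage after the change, as step 5 shows.

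**The case against.** A reader might infer that recruitment is already open to manipulation. The documents do not support that. Hub nurses deliver every session and so see assignments, but are not said to recruit. Clinic nurses screen all attending adults, but are not said to see assignments. The nearest link is that study staff take consent and the study team helps patients onto the call. Nothing says that these are the same people or that they track blocks. Aim 2 also foresees a more detailed protocol, which may settle custody of the list.

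A reader might also credit the whole drop from 20 to 1.5 to varying the sizes. Much of it is non-disclosure. Told every boundary, an observer of the variable list is still certain of about 15. Fixed blocks of 4 that were truly hidden, with only the 30/30 target known, would leave about 4/3, the certainty in the last block alone. That alternative has limited force here because 4 is printed in the protocol. For an observer who knows the set of sizes and sees the list from its start, the comparison is 20 against about 1.5.

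It is also fair that little is at stake. The illustrated bias is below the chance standard error, and the plan disclaims power and stable effect sizes. The analysis offers some protection: "This mixed-effects regression approach allows us to control for baseline outcome values that may not be balanced between groups due to small sample size". That covers measured baseline outcomes, not selection on unmeasured differences.

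**Conclusion.** The point holds as a minor design improvement. The figure of 20 is an upper case: it needs sight of the whole sequence plus knowledge of block size and position. It is about 16 without the starting position and about 1 to 7 with one central list and own-clinic sight only. No passage establishes which applies.

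Random sizes of 4, 6 and 8 bring certainty down to about 1.5 to 2.8 unless boundaries leak. Correct guesses above chance fall only 14%, so any reduction in bias is small if staff act on best guesses. The case for acting rests on the low cost of the change, not on evidence of harm.

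**What to change.** Finish any open block. Then, for participants not yet randomised, generate randomly ordered block sizes (for example 4, 6 and 8) from the same online program. Keep the sizes out of documents that recruiting staff, clinic nurses and counsellors can read. Three sizes are preferable to two: if the set and the total of 60 become known, 4 and 6 leave about 4.9 certain, and 4 and 8 about 5.6.

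- **One central list:** keep a generated list whose blocks total exactly the number still to be enrolled, which is even once the open block is complete. About 1 list in 3 qualifies for 60. The arms then end 30/30 if all enrol. Without this selection, a 60-place list is exactly 30/30 in about 73% of trials and never worse than 32/28.
- **Per-clinic lists:** balance is looser. With 3 clinics of 20 assumed, fixed blocks of 4 always give 30/30. Random sizes give it in about 46% of trials, with differences up to 8, unless each clinic's list is also chosen to total a fixed clinic target.

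Switching in mid-block would undo the balance. After 22 participants split 12/10, for example, a balanced list of 38 ends 31/29.

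The cost is regenerating the list and slightly less even flow, which is one of the stated purposes of blocking. The running difference can reach 4 instead of 2, and the longest run of intervention participants averages 3.7 instead of 3.3. Sample size, analysis and care are unchanged.

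The protocol should also state who holds the list and whether it is central or per clinic. If recruiting staff are already shielded from assignments, one sentence saying so would answer most of this point.
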